- Compare monthly RDT consumption data and volumes/TPRs reported via the registers and HMIS/DHIS2 with manual counts of used RDTs and RDT positives collected from health facilities and CHWs in monthly counts. A digital tool will be used alongside the manual counting process to take pictures of each RDT counted and provide the RDT test result.
- Identify discrepancies between reported and manual RDT counts, TPRs and ACT consumption and discuss these in monthly validation meetings.
- Observe whether discrepancies will disappear over time:

⁸ Cameroon National Malaria Control Program annual report, 2022.

⁹ Cameroon DHIS2, 2022

- Manually and digitally counted RDT volumes and positives converge with what is reported in registers/DHIS2
- Manually and digitally country RDTs and RDT positives will converge with reported RDT and ACT consumption volumes
- Assess operational feasibility, costs, and acceptability of the manual RDT storage and count method.

Participating health care workers and CHWs in study sites will be informed about the manual count and asked to store all used RDTs in labeled storage containers that will be provided for this purpose. HCW/CHW are expected to conduct business as usual, interpreting and reporting RDTs per national guidelines and recording the RDT results. At the end of each month, supervisors will collect and count the RDTs. The number of positive and total RDTs will be manually recorded and totals will be compared with the register and DHIS2 reported RDT country and positives.

Primary outcome:

• The primary outcome will be a comparison of the volume and test positivity rate (TPR) from the manual counts by trained supervisors to the TPR recorded in the HMIS (historic, surrounding areas, by CHWs and HF) on a monthly basis over the course of the 6-month intervention.

Secondary:

The secondary outcomes of this study are to:

- 1. Compare the manually counted RDTs and RDT positives to what was recorded in the registers
- 2. Compare the manually counted RDTs and RDT positives to the consumption of RDTs and ACTs recorded in the DHIS2 and pharmacy records (i.e., supply log)
- 3. Compare the costs of implementing the monthly RDT validation with potential savings from reductions in prescription of ACTs
- 4. Measure the impact of monthly RDT validation exercises on changes in HCWs' subjective norms, attitudes, perceptions and practices related to RDTs

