All health workers (n=32 - 2 per HF) and CHWs (n=31) in the Garoua Boulai health district will be approached for consent and included in the study. We anticipate collecting a minimum of 2121 tests conducted during the study period in outpatients and 1292 tests conducted in the community by polyvalent CHWs.

Inclusion/Exclusion Criteria

PARTICIPANTS- health workers in participating health facilities and CHWs in health areas (catchment) tasked to conduct the malaria RDT in patients suspected of having malaria

INCLUSION CRITERIA:

- All RDTs conducted in outpatients suspected of having malaria by participating CHWs in the targeted health area
- All RDTs conducted by participating healthcare workers on patients at the HFs
- All healthcare workers and community health workers that provided consent to participate in the study

EXCLUSION CRITERIA:

- RDTs conducted by CHWs on pregnant women (Because tests from pregnant women carried out by CHWs are not recorded in the DHIS2) or in patients
- Nonconsenting HCWs

Study Design

This is an observational pilot conducted over six months in the Garoua-Boulaï Health District. It will involve 16 health facilities and 31 CHWs routinely performing malaria testing. The selected district was selected because (i) historic testing data would suggest we could easily meet the sample size of 2121 tests in a period of 6 months in the HFs, (ii) the research team already has ongoing operations in the district, (iii) CHWs carry out Integrated Community case management (ICCM). In collaboration with district health officials and the nurse in charge of the participating health facilities, the health workers, supervisors and the community health workers in the district that conduct malaria RDTs will be invited to a short training in which the study will be explained. The health workers will be informed of the manual count of the RDTs and equipped with containers for storage of the used RDTs. They will be requested to store the used RDT readers be it positive or negative. Supervisors will collect the stored readers monthly for the manual and digital review and counting. Discrepancies will be communicated back to

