nurses in charge of the participating health facilities after each count. The supervisors and the district health official will participate in the monthly count process, facilitated and chaired by the research team (at least for the first few months). Participants in the counting process will receive brief training on manual RDT result interpretation by the research team and use of the digital tool (a mobile app downloaded on a phone).

Sampling calculation

We hypothesize that the TPR recorded in the registers differs from the TPR found through the manual count and used the anticipated difference in our sample size calculations. We calculated sample size requirements based on a cluster randomized two-sample unpaired t-test for the comparison of two proportions using standard formulae (Hayes and Bennett, 1999). We fixed the Type 1 error at 5% and the power at 80%. Prior to the intervention we assume the TPR to be 65% in HFs and 95% in CHWs. We hypothesize that this, as a result of our intervention, will decrease to 40% in HFs and 50% in CHWs. We accordingly calculated separate sample sizes for HFs and CHWs based on the baseline and expected proportions. Since we will be sampling HFs and CHWs, we expect that there will be clustering effects in the populations that these Point Of Care serve. As such, we took clustering into account by applying a design effect based on the total population (i.e. total number of tests) that these POCs cover over six months (the assumed sampling time period) - using 2023 testing data for all HFs and CHWs in East region. We used an ICC of 0.05. Based on these assumptions and calculations, the maximum sample size required for HFs and CHWs respectively is 2121 and 1292 tests. We aim to sample from 16 HFs and 31 CHWs over a single district in the East region to control unknown confounders and differences in behavior/population between HFs and CHW catchment populations.

Tools for data collection

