In Depth Interviews with participants will be conducted in designated private spaces. If a private space is not available, an alternate location will be used to maintain confidentiality. Interviews will be audio recorded, transcribed verbatim in English language. Personal identifiers such as names and phone numbers will only be collected during the informed consent process and will not be recorded during interviews. The names of health facilities will be collected during data collection for identification purposes but will be excluded during data cleaning to ensure confidentiality.

To minimize risk of disclosure to others and discrimination or stigmatization, measures will be taken to avoid loss of confidentiality. A unique identification number will be assigned to all participants. Access to the completed study instruments and databases will be limited to the project manager, project lead, and data analysts. All data files will be password - protected.

Data analysis

1. Quantitative analysis

The primary outcome will be assessed with a chi-squared test to analyze whether the difference between reported TPR and counted TPR is significantly significant. This will include outcomes for an average across all surveyed points of care (POCs), disaggregated by HFs and CHWs, and compared between baseline (pre-intervention) and endline (after six months of the intervention).

We will further investigate the difference and change in TPR by constructing a mixed effects linear regression model with the POC-month as the unit of analysis and TPR as the outcome variable. The model will include a binary indicator to exhibit pre/post intervention (implementation of the RDT check), a binary variable to indicate intervention group (i.e. "reported" or "counted" TPR), a dummy variable to exhibit month since introduction of the intervention, and a random effect variable for POC type to account for clustering. 95% confidence intervals will be fit around the TPR per POC-month.

To determine whether changes in TPR were due to changes in provider behavior or changes to the DHIS2 data, the ratio of TPRs from the health facility register to the RDT cassettes will be plotted over the six months of the intervention and compared to the change in TPR reported from the DHIS2 data.

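### The primary reported-versus-counted comparison is made while reporting is being audited and corrected, so it understates routine discordance, and its planned baseline has no cassette count

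*Protocol*

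**What the plan says.** All references are to the Protocol.

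- **Aim (AIM and Outcomes).** There are two parts: to determine how far counted and reported TPR disagree, and to explore whether comparing the sources each month improves reporting. Under the second, the team will "Observe whether discrepancies will disappear over time". The same section states that "HCW/CHW are expected to conduct business as usual".
- **Conduct (Study Design).** "The health workers will be informed of the manual count of the RDTs and equipped with containers for storage of the used RDTs". Cassettes are collected monthly, and discrepancies go back to the nurse in charge of each facility after every count.
- **Primary outcome (AIM and Outcomes).** Manual counts are compared with HMIS TPR month by month over the six intervention months. Historic and surrounding-area HMIS data are named there too, although the table under Study Outcome Measures lists them as secondary.
- **Primary test (Data analysis, Quantitative analysis).** The test is stated thus: "The primary outcome will be assessed with a chi-squared test to analyze whether the difference between reported TPR and counted TPR is significantly significant". The result is to be averaged over points of care, split by health facility (HF) and CHW, and compared between a pre-intervention baseline and an endline after six months.
- **Sizing (Sampling calculation).** "We hypothesize that the TPR recorded in the registers differs from the TPR found through the manual count", and that difference is said to drive the sample size. The inputs are then given as: "Prior to the intervention we assume the TPR to be 65% in HFs and 95% in CHWs"; and "We hypothesize that this, as a result of our intervention, will decrease to 40% in HFs and 50% in CHWs".

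**The concern.** One contrast, reported against counted TPR, serves two questions over the same months. The first is how inaccurate routine reporting is. The second is whether the audit makes it more accurate. The better the audit works, the smaller the contrast becomes, so a pooled or endline value does not answer the first question. A small difference could mean that reporting was accurate all along or that the audit corrected it, and the chi-squared test does not distinguish the two.

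The baseline does not resolve this. Reported TPR exists before the intervention, but counted TPR does not, because cassettes are stored only once the study begins. There is therefore no pre-intervention difference to compare with the endline difference.

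The results are to be presented to the national malaria programme and the Ministry, including on the accuracy of surveillance data. An understated discordance would misinform them about routine reporting.

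**Working it through.** **Step 1. What the sizing figures represent.** Inputs from Sampling calculation: 65% and 40% (HF), 95% and 50% (CHW), type 1 error 5% (two-sided assumed), power 80%, ICC 0.05, 16 HFs, 31 CHWs, 2121 and 1292 tests. The first rate in each pair is explicitly pre-intervention and the second is explicitly the level reached because of the intervention. That is a before/after contrast, while the hypothesis stated alongside it is register against count.

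**Step 2. The plan's own sample size.** Pooled two-proportion formula, per group:

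n = [1.96·√(2p̄(1−p̄)) + 0.8416·√(p₁(1−p₁)+p₂(1−p₂))]² / (p₁−p₂)²

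- HF, p̄ = 0.525: (1.384 + 0.575)² / 0.0625 = 61.4, so 62.
- CHW, p̄ = 0.725: (1.238 + 0.459)² / 0.2025 = 14.2, so 15.

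The cluster size behind the design effect is not given, so 2121 and 1292 cannot be reproduced. Nothing below depends on reproducing them.

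**Step 3. Size of the understatement.** Two assumptions: counted TPR stays at 40% (HF) and 50% (CHW), and the gap closes linearly from its full size in month 1 to zero in month 6.

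- HF: (25+20+15+10+5+0)/6 = 12.5 points, against 25 sized.
- CHW: (45+36+27+18+9+0)/6 = 22.5 points, against 45 sized.

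If the gap instead halves each month, the means are 8.2 (HF) and 14.8 (CHW).

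**Step 4. Power of a pooled six-month test.** Design effect = 1 + (m−1)·0.05, with m = tests per point of care; effective n = N / design effect. The sources are treated as independent samples, as in the plan's formula.

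| | m | Design effect | Effective n per source |
|---|---|---|---|
| HF, 2121 tests per source | 132.6 | 7.58 | 280 |
| HF, 2121 split over both sources | 66.3 | 4.26 | 249 |
| CHW, 1292 tests per source | 41.7 | 3.03 | 426 |
| CHW, 1292 split over both sources | 20.8 | 1.99 | 324 |

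| Share of gap closed | HF gap | HF power (per source / split) | CHW gap | CHW power (per source / split) |
|---|---|---|---|---|
| 50% | 12.5 | 84% / 80% | 22.5 | >99% / >99% |
| 70% | 7.5 | 43% / 39% | 13.5 | 98% / 94% |
| 80% | 5 | 22% / 20% | 9 | 75% / 63% |
| 100% | 0 | 5% | 0 | 5% |

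Under linear closure the pooled test would probably still be significant, but its estimate would be half the unaudited gap. Only an endline test after complete convergence falls to the type 1 error rate.

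**Step 5. What month 1 alone can carry.** One sixth of the minimum counts:

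- HF: 2121/6 = 353.5 tests, 22.1 per HF; design effect 1 + 21.1·0.05 = 2.05; effective n about 172.
- CHW: 1292/6 = 215 tests, 6.9 per CHW; design effect 1 + 5.9·0.05 = 1.30; effective n about 166.

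Both exceed the 62 and 15 of Step 2, so gaps of 25 and 45 points remain detectable in a single month.

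**The case against.** The plan is not blind to this. Convergence is a declared aim. Comparisons are monthly. Historic HMIS data (same month, three previous years) and surrounding districts give unaudited reported TPRs. The analysis adds a point-of-care-by-month model with terms for period, source and month. It also plots the register-to-cassette ratio over six months to separate provider behaviour from changes in DHIS2. A closed gap beside a much higher historic reported TPR would point to the audit as the cause. All of this stands and softens the concern. It does not remove it: those comparators come from other times or other sites, so they do not give discordance on the same tests, and nothing names the pre-feedback month as the discordance estimate.

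An unseen statistical analysis plan might name the month. It could not create a pre-intervention cassette count.

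Stronger readings are tempting, but the document does not support them:

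- *A successful pilot must produce a null primary test.* This needs 40% and 50% to be the counted TPR. The Sampling calculation gives them only as the level TPR should fall to and never says they are the counted rates. A null also needs essentially complete closure and an endline rather than pooled reading.
- *Power collapses.* Powers of 28% (HF) and 21% (CHW) for the six-month mean gap appear only if effective sizes are set at the values giving exactly 80% (58.7 and 11.5 per group). The plan's own counts give the much higher figures in Step 4.
- *Benin shows how fast the gap will close.* The 20-25% cited is an annual fall in cases and ACT consumption. It is not a fall in TPR over six months.
- *Every reporting worker gets feedback.* The text sends discrepancies to nurses in charge and does not say that CHWs receive them directly.

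**Conclusion.** The concern holds as a matter of bias and interpretation. Three points rest on the text alone: the primary contrast is measured under an announced count with corrective monthly feedback; the baseline value of that contrast is not available from anything described; and the sizing labels a before/after fall as a between-source difference. The size depends on two assumptions, a fixed counted TPR and the speed of convergence. With linear closure by month 6, the six-month mean is half the sized gap; slower or partial closure gives less bias. Low power is not the main problem. The change is worth making before analysis, because without it the headline difference has no single meaning.

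**What to change.** **Data analysis, Quantitative analysis.** Name two estimands.

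1. *Discordance*: reported minus counted TPR for tests done in month 1, before the first feedback, by HF and CHW. Use this as the baseline. Describe it as probably a lower bound, because workers already know of the count. Show it beside the same points of care's DHIS2 TPR before training and in the same month of earlier years. The protocol does not give DHIS2 entry timing, so note whether month-1 DHIS2 entries preceded the first validation meeting.
2. *Intervention effect*: the change in that difference from month 1 to month 6, estimated from all months, with a smaller gap as the favourable result.

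State that the pooled or endline difference is not to be read as discordance in routine reporting. Later months should still be analysed and shown.

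**Sampling calculation.** State which contrast the 65%/40% and 95%/50% figures represent.

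**Cost.** Wording, plus a stored-cassette tally from material already collected. Month 1 holds about one sixth of the tests, so its interval is wider (effective n about 172 HF and 166 CHW on the minimum counts). It covers one calendar month, and cassette retention may be less complete early on: Potential Risks plans extra storage checks in the first months. Report the monthly estimates and the share of recorded tests with a stored cassette alongside.

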2	Secondary	The proportion of RDTs reported as positive in months prior to intervention and in surrounding HF and CHWs	TPR calculated during the monthly validation meetings will be compared to the TPR found in the DHIS2 of HF in surrounding districts and in the TPR of intervention HF and CHWs attached to that HF in the same month in the three previous years.
		The total number of positive RDT found in the manual count and the total volume of ACTs administered	The total count of positive RDTs during the monthly validation meeting for each HF and CHWS attached to the HF will be compared to the total count of ACTs administered at that HF and by CHW attached to that HF during the same period, as recorded in the institution's supply log.

Total costs associated with monthly RDT counts	Collection and analysis of cost data, including personnel costs, travel expenses, and other project-related expenses will be used to estimate the total costs associated with the RDT counts
HCWs subjective norms, attitudes, perceptions and practices regarding RDT usage	A survey will be administered to participating HCWs to understand their subjective norms, attitudes, perceptions and practices regarding RDT
Acceptability and feasibility of implementing monthly RDT validation exercises	In-depth interviews will be conducted with HCWs, health officials to understand their perceptions of the acceptability of the monthly validation processes

Potential Risks

We do not foresee direct risks to participants in the study. One potential risk would be in health outcomes if fewer ACTs are administered. In Benin, where the manual count has already been rolled out, no significant impacts were recorded related to increases in morbidity and mortality in the intervention areas. The proposed intervention would not deviate from existing national guidelines in which ACTs should only be administered to patients with a parasite-based positive diagnosis (i.e., microscopy or RDT).

Loss or damage of RDT cassettes before validation is a potential risk to the study fidelity. As a mitigation, an SOP for proper storage of RDT cassettes will be provided to participating health workers for the safe handling and retention. Regular checks, especially in the first few months will also be conducted to ensure adherence to storage protocols.

Participant Enrollment and informed consent

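### The planned analysis does not estimate convergence: the reported-counted gap has no pre-intervention value, and the regression holds that gap constant over time

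*Protocol*

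**What the plan says.** The section AIM and Outcomes sets two tasks: measure how far reported and counted results disagree, and explore whether monthly comparison makes reporting more accurate. For the second, it lists "Observe whether discrepancies will disappear over time" and spells this out as "Manually and digitally counted RDT volumes and positives converge with what is reported in registers/DHIS2".

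Counted data begin with the study. Under Study Design, staff are trained and then "The health workers will be informed of the manual count of the RDTs and equipped with containers for storage of the used RDTs"; discrepancies are reported back to the nurses in charge after each monthly count. The earlier data named in the Study Outcome Measures table are of another kind. Counted TPR is set against surrounding districts and "in the TPR of intervention HF and CHWs attached to that HF in the same month in the three previous years", which is reported TPR with no cassette count behind it.

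Under Data analysis, 1. Quantitative analysis, a chi-squared test of reported against counted TPR is to be "compared between baseline (pre-intervention) and endline (after six months of the intervention"). The regression is introduced with "We will further investigate the difference and change in TPR". Its listed terms are a pre/post indicator, a source indicator (reported or counted), "a dummy variable to exhibit month since introduction of the intervention", and a random effect for type of point of care (POC). No interaction is listed. The same section plans a plot of the facility register-to-cassette TPR ratio over the six months.

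**The concern.** Convergence is a statement about how the reported-counted gap changes with time. Two planned analyses appear to address it, and neither does. The baseline-to-endline comparison needs a counted TPR from before the intervention, which the design does not produce. The regression has a parameter for the average gap but none for a change in it, so its source coefficient mixes month 1, before any feedback, with the months after feedback.

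At stake is the answer to whether monthly counting improves reporting. The dissemination plan takes the findings to the national malaria programme and the Ministry of Health and mentions scale-up. As written, the study would report how large the average gap was, but give no estimate, with its uncertainty, of whether the gap closed.

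**Working it through.** **Step 1. Is there a baseline gap?** Gap = reported TPR minus counted TPR. Before the intervention, reported TPR is available (DHIS2, previous years) but counted TPR is not, because no cassettes were kept. The pre-intervention gap is therefore undefined.

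The same result appears in the regression. Take six pre-intervention months with reported TPR only (six is an assumption; any number gives the same result) and six intervention months with both sources. Counted = 1 occurs only where post = 1, so the product post x counted is the same column as counted. Ranks of the fixed-effects design matrix:

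| Terms | Columns | Rank |
|---|---|---|
| Intercept, post, source, months 2-6 (month 1 as reference) | 8 | 8 |
| The same plus post x source | 9 | 8 |
| Intercept, post, source, all six month dummies | 9 | 8 |
| First row plus source x linear month | 9 | 9 |

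The change in gap from before to after the intervention (row 2) is not estimable. A trend in the gap across months 1-6 (row 4) is.

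**Step 2. What gap does the listed model allow?** Write TPR = b0 + b1(post) + b2(counted) + month effect. In any intervention month, reported minus counted = -b2. The post and month terms cancel because they shift both sources equally, whether month is coded as dummies or as a number. The random effect for POC type cancels for the same reason. With both sources observed in each month, b2 is minus the mean of the six monthly gaps.

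**Step 3. Illustration.** Sampling calculation gives facility TPRs of 65% before and 40% after. The two hypothetical courses below start from a pre-intervention reported TPR of 65%.

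| Month | 1 | 2 | 3 | 4 | 5 | 6 |
|---|---|---|---|---|---|---|
| A reported | 65 | 60 | 55 | 50 | 45 | 40 |
| A counted | 40 | 40 | 40 | 40 | 40 | 40 |
| A gap | 25 | 20 | 15 | 10 | 5 | 0 |
| B reported | 58.75 | 56.25 | 53.75 | 51.25 | 48.75 | 46.25 |
| B counted | 46.25 | 43.75 | 41.25 | 38.75 | 36.25 | 33.75 |
| B gap | 12.5 | 12.5 | 12.5 | 12.5 | 12.5 | 12.5 |

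Mean gap in A: (25 + 20 + 15 + 10 + 5 + 0)/6 = 12.5, as in B. The average of the two sources in each month is also the same in A and B (52.5, 50, 47.5, 45, 42.5, 40). Noise-free fits of the listed model return identical coefficients: source -12.5, post -6.25, months 2-6 from -2.5 to -12.5. With a source x linear month term, the slope of counted minus reported is +5.0 points per month in A and 0 in B.

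For CHWs (95% and 50%), a gap falling from 45 to 0 and a gap fixed at 22.5 both give a source coefficient of -22.5; with the added term the slopes are +9.0 and 0.

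**Step 4. Precision given up.** Suppose the six monthly gap estimates are independent with equal variance v (an assumption). The pooled gap has variance v/6. Month 6 minus month 1 has variance 2v, so its standard error is sqrt(2 x 6) = 3.5 times as large. Five times the fitted slope has variance 25v/17.5 = 1.43v, where 17.5 = 2(2.5² + 1.5² + 0.5²); its standard error is sqrt(1.43 x 6) = 2.9 times as large.

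**The case against.** Most of the case against concerns how far the point reaches, and much of it stands.

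- A reader might infer that convergence cannot be tested at all. The documents do not support that: both sources are recorded monthly for six months, and row 4 of the table shows a trend in the gap is estimable. Only the change from before the study is out of reach.
- Convergence is one of two aims, in what the protocol calls a pilot: "This is an observational pilot conducted over six months in the Garoua-Boulaï Health District". The primary outcome, the monthly comparison of counted with HMIS figures, does not depend on this point.
- The gap is not ignored over time. The Study Outcome Measures table plans monthly comparisons, and the ratio plot follows the gap directly. Both are descriptive; the plot names only the health facility register, and neither has an estimate or interval for change.
- A reader might infer that the model is not estimable. That holds only if all six month dummies enter beside pre/post; with a reference month the model is full rank, and the source coefficient is estimable either way.
- A reader might infer that a non-significant endline test will be taken as convergence. Nothing in the protocol says so.
- The baseline sentence could be meant for reported TPR alone, which is feasible. But it follows directly on the reported-against-counted test and does not say this.
- An analysis plan not shown here could add an interaction. The protocol nevertheless lists its model terms and states a comparison that its design cannot supply, so the text needs correcting in either case.

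**Conclusion.** The point holds in this limited form: as written, the analysis does not estimate convergence. The reported-counted gap has no pre-intervention value, and the listed main effects impose one constant gap. Full convergence from 25 points and no convergence at 12.5 points can be indistinguishable in facilities; for CHWs the same is true of 45 to 0 and 22.5.

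The conclusion assumes that the listed terms are the whole fixed part of the model and that no cassettes were kept and counted before the training. The size of the illustration rests on a hypothetical linear decline built from the protocol's planning figures; the constant-gap result does not. The measurement of average discordance is unaffected.

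**What to change.** 1. Add a source-by-month interaction over months 1-6, and report the change in the gap (month 6 minus month 1, or the monthly slope) with a 95% CI, for facilities and CHWs separately.
2. Restrict the pre/post comparison to reported (register/DHIS2) TPR, and reword the baseline sentence accordingly.
3. Describe month 1 as the first counted point: before feedback, but after staff were told of the count. It is not a true pre-intervention baseline.
4. If month is coded as dummies, name a reference month so that they are not collinear with pre/post.
5. Keep the ratio plot as the descriptive companion to the estimate.

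The cost is wording only; no new data are needed. There are two downsides. The change in the gap is less precise than the pooled gap (standard error roughly three times as large under the simple assumption in the working). Any shift in reporting caused by announcing the count is not captured, and the report should say so.
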